3.1 Study Design

This study will be a randomized, unblinded, three-way crossover study to determine naloxone plasma concentration after administration of multiple doses of intranasal (IN) naloxone.

Table 3-1: Study Schedule

Day -1	Day 1	Days 2-3	Day 4	Days 5-6	Day 7	Day 8
Check-in	Treatment Period 1	Washout	Treatment Period 2	Washout	Treatment Period 3	Check-out

The following 3 treatments will be evaluated in a randomized order over the 3 treatment periods.

Table 3-2: Study Treatments

Treatment	Description
A	Four 4 mg IN naloxone doses (1 dose every 2.5 min; L at 0 min, R at 2.5 min, L at 5 min, R at 7.5 min)
B	Four 4 mg IN naloxone doses (2 doses every 2.5 min; L and R at 0* min, L and R at 2.5* min)
C	Two 4 mg IN naloxone doses (L at 0 min, R at 2.5 min)

*L = Left Nostril, R = Right Nostril, * doses will be ~5 seconds apart (one after the other)*

Healthy subjects will be randomized to one of six treatment sequences (i.e., ABC, ACB, BAC, BCA, CAB, CBA). FDA will prepare the randomization schedule. Subjects will report to the study site for screening from Days -28 to -2 and then will return to the site on Day -1 for baseline assessments and check-in. After check-in (Day -1), subjects will receive dosing for the 3 respective treatment periods on Days 1, 4 and 7. There will be two days of washout between each treatment period. Participants will be confined in the study clinic from Day -1 until the morning of Day 8. On dosing days, dosing will occur as per the treatment description and PK assessments will occur at the following time points:

- PK assessment: 0 (pre-dose), 2, 4.5, 7, 10, 12.5, 15, 20, 30, 45, 60, 120, 180, 240, 360, and 720 minutes

The subject should remain fully supine for approximately one-hour post-dose. Subjects should be instructed not to breathe through the nose during administration of the nasal spray into the nose. Subjects will be instructed to leave their masks off for twenty minutes after drug administration.

A summary of all assessments prior to and following study drug administration on Day 1, is described in the Protocol, Schedule of Events.

Subjects will be discharged from the study after completion of all study procedures. If a subject discontinues from the study prematurely, all procedures scheduled for the end of the study will be performed.

4. Study Endpoints

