Based on these considerations and the concentration ratios and CVs in Table 4-1, a sample size was determined so that at least one of the planned time points would have greater than 90% power at a 0.0221 significance level for a one sided, log-transformed paired comparison (for the primary endpoint). For concluding an increase in naloxone concentration for Treatment A compared to Treatment C at 15 minutes, at least 12 subjects would be necessary assuming a 1.78-fold increase in exposure and 48% CV for the treatments. For concluding an increase in naloxone concentration for Treatment B compared to Treatment C at 10 minutes, at least 12 subjects would have the desired power assuming a 2-fold increase in exposure and 68% CV for the treatments. The sample size was further increased to 20 subjects to account for discontinuations and situations where the CV values in Table 4-1 may be underestimated for repeat naloxone dosing.

5. Analysis Populations

The PK population will include all subjects who receive study drug and have at least one estimable PK parameter after dosing. The safety population will include all subjects who receive

at least 1 dose of the study drug. The analysis population will include all subjects in the PK population with sufficient data to calculate PK parameters. Only subjects with results from two or more periods will be included in comparisons. Treatment in all analysis populations will be assigned based upon the treatment which the subjects actually received.

6. Data Screening and Acceptance

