subjects contributing naloxone concentration measures from both treatments at the pre-specified time points will be included in the analysis. At each of these timepoints, subject-level naloxone concentration will be log-transformed. Naloxone concentration values that are below the lower limit of quantification (i.e., zero) will result in that time point from that subject being removed for comparisons involving that treatment arm.

A paired Student's t-test will be used for comparing naloxone concentrations between treatments. To demonstrate an increase in naloxone concentration with the test compared to reference, it is necessary that the lower bound of the one-sided 97.79% interval for the geometric mean ratio excludes 1. The results will be transformed back to the original scale by exponentiation to provide treatment geometric means.

Normality assumption will be verified using the Shapiro-Wilke test for normality and homogeneity of variances will be verified using Levene's test. If either assumption is not valid, a Mann-Whitney-U test will be used for the comparisons rather than a t-test.

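### The fallback for the paired primary comparison is an unpaired test, and a variance check that a paired t-test does not need can trigger it

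*SAP*

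**What the plan says.** The design is a crossover in which every subject receives all three treatments (SAP 3.1: "This study will be a randomized, unblinded, three-way crossover study to determine naloxone plasma concentration"). SAP 7.3.1 keeps only complete pairs at each time point: "subjects contributing naloxone concentration measures from both treatments at the pre-specified time points will be included in the analysis". The test matches that design: "A paired Student's t-test will be used for comparing naloxone concentrations between treatments". Success requires the one-sided 97.79% lower bound for the geometric mean ratio to lie above 1.

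The same section then adds two checks. Normality is tested by Shapiro-Wilk, and "homogeneity of variances will be verified using Levene's test". The consequence of failing either one is: "If either assumption is not valid, a Mann-Whitney-U test will be used for the comparisons rather than a t-test".

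The section gives no significance level for the checks. It does not say whether Shapiro-Wilk is applied to each arm or to the within-subject differences. It applies the same approach to the secondary B versus A comparison, so the rule governs all nine planned tests.

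SAP 4.4 sizes the study "for a one sided, log-transformed paired comparison (for the primary endpoint"). Protocol 4.9.5 names no test, and Protocol 4.9.1 (Analysis Populations) lets the SAP prevail. Neither document offers a paired rank test.

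**The concern.** There are three faults in the rule.

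- **Wrong fallback.** Mann-Whitney U treats the two sets of concentrations as coming from different people. Between-subject variation, which pairing removes, returns to the comparison.
- **Wrong trigger.** A paired t-test needs roughly normal within-subject differences. Equal arm variances are not one of its assumptions, and Levene's test itself presumes independent groups. A Levene failure can therefore move the primary analysis from a valid test to a mismatched one.
- **Incomplete rule.** Without levels for the checks, or a stated target for Shapiro-Wilk, two analysts could reach different primary tests from the same data. Mann-Whitney also does not give the paired geometric mean ratio interval on which success is defined.

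The endpoint is the first time point with a higher concentration, and testing stops at the first success. The chance of reporting the earliest time point is therefore exactly the power at that first test, and that is where the fallback loses most in A versus C and B versus C.

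**Working it through.** **Inputs from the documents.** n=18 per comparison (Protocol 4.9.1, Sample Size; SAP Table 4-1); one-sided level 0.0221; ratios and CVs from SAP Table 4-1.

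**Assumptions, none given in the documents.** Within-subject correlation ρ, 0.05 for each check, tail shape, and ratio of arm SDs.

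**Step 1: reproduce Table 4-1.** Let σ = √ln(1+CV²). If σ is the log SD per treatment, the SD of the paired difference is σ√(2(1−ρ)), which equals σ at ρ = 0.5. Power is P(T > 2.173), where T is noncentral t with 17 df and noncentrality ln(ratio)·√18/σ.

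Example, A versus C at 15 min: σ = √ln(1+0.48²) = 0.455. Noncentrality = 0.5766 × 4.243/0.4553 = 5.37, which gives 99.9% (SAP: 100).

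All nine rows reproduce. At ρ = 0 they do not: A versus C gives 27/64/94% and B versus C gives 57/70/88%.

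**Step 2: power once the fallback is in use.** Normal log pairs were simulated with ρ = 0.5 and equal variances, 10,000 runs per row. The exact critical values are U ≥ 226 for Mann-Whitney (level 2.18% for independent samples) and W ≥ 132 for signed-rank (2.16%).

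| Comparison | Min | Ratio | CV % | σ | SAP power % | Paired t, computed % | Signed-rank % | Mann-Whitney % |
|---|---|---|---|---|---|---|---|---|
| A vs C | 10 | 1.36 | 68 | 0.617 | 49 | 49.1 | 47 | 21 |
| A vs C | 12.5 | 1.57 | 58 | 0.538 | 91 | 90.7 | 89 | 69 |
| A vs C | 15 | 1.78 | 48 | 0.455 | 100 | 99.9 | 99.8 | 98 |
| B vs C | 4.5 | 2 | 111 | 0.896 | 86 | 85.8 | 84 | 60 |
| B vs C | 7 | 2 | 90 | 0.770 | 94 | 94.2 | 93 | 76 |
| B vs C | 10 | 2 | 68 | 0.617 | 99 | 99.3 | 99 | 94 |
| B vs A | 4.5 | 2 | 111 | 0.896 | 86 | 85.8 | 85 | 61 |
| B vs A | 7 | 1.85 | 90 | 0.770 | 88 | 87.9 | 86 | 64 |
| B vs A | 10 | 1.47 | 68 | 0.617 | 68 | 68.4 | 66 | 38 |

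The SAP's sizing target, more than 90% power at one planned time point, still holds at A versus C 15 min and B versus C 10 min.

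**Step 3: dependence on ρ.** The SD of the difference is held at the value that reproduces Table 4-1, so paired-t power stays fixed.

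| Mann-Whitney | ρ = 0 | 0.25 | 0.5 | 0.75 |
|---|---|---|---|---|
| Power %, A vs C 10 min | 47 | 37 | 22 | 5 |
| Power %, A vs C 15 min | 99.8 | 99.8 | 98.5 | 83 |
| Power %, B vs C 4.5 min | 86 | 78 | 60 | 22 |
| Power %, B vs C 10 min | 99 | 98 | 95 | 69 |
| True size % (nominal 2.21) | 2.1 | 1.1 | 0.4 | 0.0 |

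Almost nothing is lost at ρ = 0. At ρ = 0.75 the sizing target fails in both primary comparisons.

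**Step 4: the whole procedure.** As written, a failure of Shapiro-Wilk (run on differences) or of median-centred Levene leads to Mann-Whitney; otherwise the paired t-test is used. As fixed, a Shapiro-Wilk failure leads to signed-rank; otherwise the paired t-test is used. ρ = 0.5 throughout.

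| Data | Fallback fires | A vs C 10 min, written vs fixed % | B vs C 4.5 min, written vs fixed % |
|---|---|---|---|
| Normal, equal SD | about 7% | 46.8 vs 48.8 | 83.6 vs 85.4 |
| Normal, test-arm SD 1.5× reference | 27–29% | 27.0 vs 31.7 | 56.4 vs 63.6 |
| Normal, test-arm SD 0.67× reference | 27–29% | 51.2 vs 59.7 | 87.8 vs 93.9 |
| Normal, SD ratio 2, SD of difference as in Table 4-1 | 67–69% | 35.1 vs 48.9 | 71.3 vs 85.7 |

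In the three unequal-SD rows the differences are still normal and the paired t-test remains valid; Levene causes most of the switches. In the equal-SD case the largest loss among the time points examined is 2.2 points (B versus A at 10 min, 66.5 vs 68.7). At A versus C 15 min with SD ratio 2 the figures are 98.8 vs 99.9.

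**The case against.** The strongest reply is that the error hardly matters under the SAP's own model. Table 4-1 gives one CV per row, so the plan assumes lognormal data with equal variances. The fallback then fires in about 7% of tests and costs about 2 points. The primary test is right, the sizing target survives at ρ = 0.5, and no false claim of a higher concentration is at stake. All of this stands, and it limits the severity.

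Other points also have force:

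- **Correlation is not identified.** Table 4-1 reproduces equally well if the CV is taken as describing the within-subject difference, which says nothing about ρ. Step 3 shows how widely the loss varies. The phrase "assuming a 1.78-fold increase in exposure and 48% CV for the treatments" favours the per-treatment reading but does not settle it.
- **Nothing in the documents predicts unequal variances.** The SAP allows for "situations where the CV values in Table 4-1 may be underestimated for repeat naloxone dosing", but that is about larger CVs, not CVs that differ between arms.
- **Losses at the last time points are smaller.** At A versus C 15 min the loss is about 0.1 points with a 0.67× SD ratio. With 1.5× it is about 5 points, leaving power at 91%.
- **With heavy tails the rule does little harm.** With t-distributed log data (3 df, rescaled to the same SD), the rule as written roughly matches or beats a plain paired t-test: 62.8 vs 62.9 at A versus C 10 min, and 91.8 vs 88.4 at B versus C 4.5 min. It trails the signed-rank version by 7.7 and 2.6 points.
- **The full distribution of the reported first time point was not computed.** For the earliest time point in each sequence, however, single-test power is that probability.

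None of this makes an independent-samples test suitable for paired data, or makes Levene's test relevant to a paired t-test.

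**Conclusion.** The concern holds and should be fixed before concentration data are available. The rule names the wrong test for paired data and lets an irrelevant check invoke it, in the primary analysis and in the secondary B versus A comparison.

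The expected cost is small if log concentrations are normal with equal variances, and moderate at the early time points if arm variances differ. With positive correlation the error goes one way only: a later or missed first time point, with no inflation of false positives. These sizes rest on the assumed ρ = 0.5, 5% checks and the SD ratios shown. The mismatch between test and design rests on none of them.

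**What to change.** Amend SAP 7.3.1 as follows:

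1. Replace Mann-Whitney U with the exact Wilcoxon signed-rank test on within-subject log differences. Report the exponentiated Hodges-Lehmann estimate with a one-sided lower bound. At n=18 the nearest exact level is 97.84% (1 − 0.0216), against the SAP's 97.79%.
2. Apply Shapiro-Wilk to the within-subject differences and state its level.
3. Delete the Levene's test trigger.

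Signed-rank assumes roughly symmetric differences, so it does not fully answer a normality failure caused by skewness. A simpler option that also avoids choosing the test from the data is to keep the paired t-test throughout and report signed-rank as a sensitivity analysis.

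The cost is two or three sentences, with no new data or subjects. When the fallback is used on normal log data, signed-rank gives up at most about 3 power points against the paired t-test.

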7.3.2 Dose Proportionality

Dose proportionality based on C_{max} , AUC_{0-t} , and AUC_{0-inf} will be compared between each of the three naloxone treatments as secondary endpoints. The 4-dose naloxone arms (separate comparisons for 1 dose every 2.5 minutes and 2 doses every 2.5 minutes) will be compared with the 2-dose naloxone arm (1 dose every 2.5 minutes). An additional comparison will be performed between the 4-dose naloxone arm B (2 doses every 2.5 minutes) as test and 4-dose naloxone arm A (1 dose every 2.5 minutes) as reference.

Dose-adjusted values for C_{max} , AUC_{0-t} , and AUC_{0-inf} will be calculated based on noncompartmental PK parameter results, normalized to per mg of naloxone administered. Using linear mixed-effects modeling, comparisons of log-transformed dose-adjusted PK parameters will be performed. Treatment will be a fixed effect. Subject will be included as a random effect on the intercept. Treatment differences on the log-scale will be estimated for the PK parameters. Geometric mean ratio and 90% CIs will be obtained by exponentiation of the treatment effect and 90% CIs based on the log-transformed scale. Dose-proportionality will be concluded if the confidence interval includes 1.

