4.9.5 Pharmacokinetic Analysis

Pharmacokinetics: Concentrations will be determined at specified times. The primary endpoint is the first timepoint when there is a higher naloxone plasma concentration in the 4 naloxone dose arms compared to the 2 naloxone dose arm. The comparisons will consider multiple, pre-specified timepoints and adjust for multiplicity using Pocock boundaries. Separate comparisons will be performed looking at the 4 naloxone dose arm A (test) versus the 2 naloxone dose arm C (reference) and the 4 naloxone dose arm B (test) versus the 2 naloxone dose arm C (reference). Different timepoints will be selected for each comparison and timepoints will be evaluated from earliest to latest time.

Secondary endpoints will include determination of the first timepoint when there is a higher naloxone plasma concentration in the 4 naloxone dose arm B (2 doses every 2.5 minutes) as test compared to the 4 naloxone dose arm A (1 dose every 2.5 minutes) as reference. The same approach as outlined for the primary endpoint analysis above will be used for this comparison.

Additional PK measures (i.e., C_{max} , AUC_{0-inf} , AUC_{0-t} , pAUC, T_{max} , half-life, elimination rate) will be exploratory endpoints and determined for each subject using non-compartmental

methods. All parameters will be calculated using SAS or R software and will be reported with standard descriptive statistics including the mean and coefficient of variation. Calculation of PK parameters will be performed using actual sampling times. Additional details of the PK analysis will be included in the SAP.

Dose Proportionality: Dose proportionality based on C_{max} , AUC_{0-t} , and AUC_{0-inf} will be compared between each of the three naloxone treatments as secondary endpoints. The 4 naloxone doses arms (separate comparisons for 1 dose every 2.5 minutes and 2 doses every 2.5 minutes) will be compared with the 2 naloxone dose arm (1 dose every 2.5 minutes). An additional comparison will be performed between the 4 naloxone arm B (2 doses every 2.5 minutes) as test and 4 naloxone dose arm A (1 dose every 2.5 minutes) as reference.

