4.2 Secondary Endpoints

1. First time point when there is a higher naloxone plasma concentration in the 4-dose naloxone arm B (2 doses every 2.5 minutes) compared to the 4-dose naloxone arm A (1 dose every 2.5 minutes)
2. Dose-proportionality of the 4-dose naloxone arms in reference to the 2 -dose naloxone arm based on C_{max} , AUC_{0-inf} and AUC_{0-t}
3. Predicted time to rescue a patient from simulated opioid-induced respiratory depression from fentanyl and carfentanil following medium and high overdose scenarios

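### SAP 7.3.2 does not exclude the equal-dose pair B vs A from its dose-proportionality conclusion rule, although that pair cannot by itself establish proportionality

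*SAP*

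**What the plan says.** SAP 4.2 defines the secondary endpoint as "Dose-proportionality of the 4-dose naloxone arms in reference to the 2 -dose naloxone arm", based on Cmax and the two AUCs. Protocol 3.2 says the same. Neither mentions B vs A.

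SAP 7.3.2 is wider. It opens: "Dose proportionality based on C_{max} , AUC_{0-t} , and AUC_{0-inf} will be compared between each of the three naloxone treatments as secondary endpoints". It names A vs C and B vs C, then continues: "An additional comparison will be performed between the 4-dose naloxone arm B (2 doses every 2.5 minutes) as test", with arm A as reference. Parameters are "normalized to per mg of naloxone administered", log-transformed, and compared in one mixed model with a fixed treatment effect and a random subject intercept. "Geometric mean ratio and 90% CIs will be obtained by exponentiation of the treatment effect" and its interval. The section ends: "Dose-proportionality will be concluded if the confidence interval includes 1". No sentence limits that rule to named pairs, and none says expressly that the B vs A result will carry the label.

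Protocol 4.9.5 also lists the pair ("An additional comparison will be performed between the 4 naloxone arm B (2 doses every 2.5 minutes) as test"), as does the protocol synopsis, but the protocol contains no rule for concluding proportionality. The second section numbered 4.9.1 in the protocol (Analysis Populations) gives the SAP precedence over the protocol on planned analyses.

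**The concern.** Dose proportionality asks whether exposure per mg is the same at two different doses. A and B give the same dose on different schedules, so their ratio has no dose contrast in it.

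The protocol's Introduction anticipates that re-dosing a nostril may lose exposure. Both 4-dose arms re-dose both nostrils. If they lost the same share, B/A would stay at 1, and a literal analyst would write dose-proportional beside B vs A while the comparisons with C pointed the other way. Conversely, if the schedules gave different exposure at the same dose, the label would be withheld for a reason unrelated to dose.

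This is separate from whether an interval that includes 1 is good evidence of proportionality. Replacing that rule with an equivalence margin would not help here: with tight data, B vs A could pass firmly while both arms were equally under-proportional. At stake is one label on a secondary analysis.

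**Working it through.** **The plan's own figures.** The documents give no operating figure for the proportionality rule. The nearest is the power in SAP Table 4-1 for the concentration tests. A one-sided paired t-test on the log scale, with n = 18, alpha = 0.0221 and SD of the paired difference = sqrt(ln(1 + CV²)), gives 85.8%, 87.9% and 68.4% for B vs A at 4.5, 7 and 10 min. The table states 86, 88 and 68. All nine entries reproduce within 0.5 point. That power does not bear on the rule examined here.

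**Dose contrast** (doses from SAP Table 3-2).
- A: 4 × 4 = 16 mg. B: 4 × 4 = 16 mg. C: 2 × 4 = 8 mg.
- Dose-adjusted A/C = (A/16)/(C/8) = A/(2C), and likewise for B/C. The dose enters these ratios.
- Dose-adjusted B/A = (B/16)/(A/16) = B/A. The dose cancels.

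**What B/A can and cannot show.** On dose-adjusted values, B/A = (B/C)/(A/C).
- Both arms proportional: 1.0/1.0 = 1.
- Both at 70% of proportional exposure: 0.7/0.7 = 1.

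The two situations give the same B/A, so no interval for B/A, however narrow, can separate them. Unequal departure, for example 0.8/0.6 = 1.33, does show in B/A, but only as a difference between schedules.

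**How often the label would appear on a literal reading.** If true B/A is 1, a 90% interval includes 1 in 90% of trials by definition. As a check, the SAP model was simulated as a balanced within-subject analysis of variance, with 20,000 trials per setting. The documents do not give a within-subject CV for Cmax or AUC, so a range of 20% to 60% was assumed. Results for n = 18 and a true dose-adjusted A/C = B/C = 0.7 (a hypothetical common loss):

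| Assumed CV | B vs A includes 1 | A vs C includes 1 | B vs C includes 1 | B vs A includes 1, both C comparisons exclude 1 |
|---|---|---|---|---|
| 20% | 89.6% | 0.0% | 0.0% | 89.6% |
| 30% | 90.0% | 2.7% | 2.7% | 86.5% |
| 40% | 89.8% | 14.3% | 13.7% | 71.5% |
| 50% | 89.7% | 28.5% | 28.4% | 54.3% |
| 60% | 90.2% | 40.3% | 40.6% | 41.6% |

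Over all settings run (n = 18 and 20; common true ratios to C of 1.0, 0.8, 0.7, 0.6 and 0.5), the B vs A column stays between 89.5% and 90.4%. It does not depend on the assumed CV or on the true ratio to C. The other three columns do.

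**Number of conclusions.** Literal 7.3.2: 3 pairs × 3 parameters = 9, of which 3 are B vs A. Under the SAP 4.2 definition: 2 pairs × 3 parameters = 6, none of them B vs A.

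**The case against.** The strongest reply is that SAP 4.2 already settles the scope. The endpoint is defined against the 2-dose arm, and both documents set B vs A apart as an additional comparison. On that reading the rule covers only A vs C and B vs C, and nothing is wrong. This has force: a reader might infer that the SAP will certainly declare proportionality for B vs A, and the documents do not say so. But 7.3.2 says that proportionality "will be compared between each of the three naloxone treatments as secondary endpoints" and then gives an unrestricted rule. The precedence clause in the protocol cannot resolve a difference between two sections of the SAP, so the ambiguity stands.

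Other stronger inferences fail:
- **B vs A is worthless here.** It is not. As the quotient of B/C and A/C, it shows whether departure from proportionality differs by schedule, a sensible reason to estimate it in the same model.
- **Re-dosing affects A and B alike.** The documents do not say this. The protocol names both close timing and same-nostril dosing as possible causes. The same nostril is re-dosed after 5 min in A and 2.5 min in B, and B's paired sprays are about 5 seconds apart. Equal loss is only an assumption.
- **The results would contradict one another.** A/C below 1, B/C below 1 and B/A equal to 1 are mutually consistent. Only the word attached to the third would mislead.
- **Under-proportionality would be hidden.** A vs C and B vs C are each judged separately against C.

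It is also fair to say that the 90% is simply nominal coverage, and that correcting the label changes no number.

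**Conclusion.** The point holds as a minor one. SAP 7.3.2 leaves B vs A inside a conclusion rule that this pair cannot support, and SAP 4.2 points the other way. Followed literally, the rule would attach an unsupported dose-proportionality label to B vs A in about 90% of trials for each parameter. This rests on the literal reading of 7.3.2 and on a true B/A of 1. In the remaining 10% or so the interval excludes 1 by chance. If the schedules truly differ in exposure, the 90% figure does not apply, but the label would still not describe dose.

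The frequency of discordant labels (86.5% at n = 18, CV 30% and a common ratio of 0.7) depends on the assumed CV and loss and is illustrative only. No estimate, interval, A vs C or B vs C result, primary endpoint or sample size is affected.

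**What to change.** In SAP 7.3.2, state that the dose-proportionality conclusion applies only to A vs C and B vs C, in line with SAP 4.2. State that B vs A is an equal-dose comparison of schedules, reported as a geometric mean ratio with its 90% interval and without a dose-proportionality statement. Dose-adjusted or unadjusted parameters may be used for this pair, since the ratio is identical.

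The cost is about two sentences and an entry in the SAP change log, with the same model and output. On a literal reading, the B vs A label falls from about 90% of trials (true B/A = 1) to none. No protocol amendment is needed: the protocol does not contain the conclusion rule and defers to the SAP on planned analyses. An amendment would also require IRB approval under Protocol 7.3.1.
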